### **5.10 Randomization and Blinding**

Eligible patients will be randomly assigned to treatment in a 1:1 ratio to receive either INL-001 or placebo collagen implants. Patients will not be aware of their treatment allocation and all study staff involved in efficacy and safety assessments will be blinded to treatment assignments until after database lock and release of unblinding randomization codes. Emergency unblinding is allowable if deemed necessary by the investigator, and discussed and agreed with the study medical monitor, for the safety of the patient and will be fully documented and included in protocol deviations. Patients will be stratified by study center and body mass index (BMI) ( $<30 \text{ kg/m}^2$  and  $\geq 30 \text{ kg/m}^2$ ). In the case of a suspected unexpected serious adverse reaction (SUSAR), unblinding of the sponsor will be performed according to the safety management plan.

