### **9.1 Sample Size and Power Considerations**

The sample size was chosen primarily on the basis of previous clinical study data for INL-001 in inguinal hernia repair, but also with the consideration of the results of other bupivacaine-containing products studied in abdominoplasty. Sample size is estimated at 360 patients, with 180 patients per treatment group. The effect size with INL-001 in the combined results of 2 clinical Phase 3 studies in postoperative analgesia after open inguinal hernia repair was 0.525 for SPI24. The effect size with INL-001 for SPI48 was 0.25. With the historical SPI48 effect size of 0.25, 360 evaluable patients will yield a power of at least 66%; however, it is believed that a greater separation between the INL-001 and placebo treatment groups will be observed for abdominoplasty given that postoperative pain is more severe and longer lasting than with inguinal hernia repair, yielding greater power. This is increased to 372 patients to potentially counter the effects of imputation for dropouts, but all randomized and treated patients will be evaluable and included in the modified intent-to-treat (mITT) analyses.

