If a patient withdraws from the study and does not continue to provide pain assessments or has no values following a missing/censored 24-hour value, multiple imputation methods will be employed using observed data and reason for withdrawal. First, all pain intensity values will be assigned to their nominal time points for the purposes of creating covariates for the multiple imputation; when a rescue medication was used, the scheduled values that fall in the censoring period will be replaced with the “pain right now” collected prior to the rescue use. This substitution will be employed only for executing the multiple imputation (MI) procedure for imputing values after withdrawal; the methods above will be used for the actual SPI calculation. Data for patients who discontinued early due to lack of efficacy or an adverse event(s) will be imputed using the distribution of the worst values observed to that point, conditioned on the nonmissing values. For patients who discontinue for any other reason, values will be imputed assuming missing at random; covariates will include all nonmissing pain-intensity assessments and imputation will be done within treatment group. For the multiple imputation stages, values will be imputed using 20 replicates and the Markov Chain Monte Carlo (MCMC) method implemented with the SAS (Statistical Analysis Software®) MI procedure. Patients who are

Innocoll

Clinical Study Protocol With Amendment 02

Study INN-CB-024

Controlled Study-Postsurgical Analgesia

missing their 0.5-hour and/or 1-hour values will have that value imputed as the first nonmissing value and the SPI will be calculated as described. Full details of the SPI calculations will be in the SAP, including sensitivity analyses to test the robustness of the assumptions.

All efficacy comparisons will be based on the comparison of INL-001 vs placebo.

The primary efficacy variable, SPI24, will be analyzed using an analysis of covariance (ANCOVA) model with treatment as the main effect and a covariate for BMI (continuous). Summary statistics (sample size, mean, SD, median, minimum, maximum, and 25th and 75th percentiles) will be presented along with the least squares (LS) mean, standard error (SE), 95% CIs, difference in LS means, and p-values from the ANCOVA model.

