To account for the interim analysis and potential sample size increase, the method of [Cui et al 1999](#) will be employed. For the final analysis and resulting p-value, the data will be split for those patients included in the interim analysis and those not included in the interim analysis; data from these groups will be analyzed completely independently, then combined using the inverse normal method to test the null hypotheses that there is no difference between the treatment groups:

$$Z_1 = \Phi^{-1}(1 - p_1)$$

$$\text{and } Z_2 = w_1 Z_1 + w_2 \Phi^{-1}(1 - p_2)$$

where:

$Z_1$ =the Z statistic for the first stage

$Z_2$ =the combination test statistic at the end of the second stage

$w_i$ =the weighting applied for each associated Z statistic

$p_1$ =the first stage p-value

$p_2$ =the second-stage p-value based on second-stage participants

For maximum statistical efficiency, the weights are defined prospectively according to the square root of the planned proportion of participants in the 2 stages, relative to the preplanned total enrollment of 360 patients, as  $w_i = \sqrt{0.5}$ . The calculation of these weights is fixed and will not be changed due to unblinded data; likewise, in the case of deviations from the planned proportions due to enrollment overrun (see interim analysis section below), the weights will remain fixed.

The key secondary efficacy variables include:

- SPI from Time 0 through 48 hours (SPI48)
- proportion of patients who are opioid free posttreatment through 24 hours
- proportion of patients who are opioid free posttreatment through 48 hours
- SPI from Time 0 through 72 hours (SPI72)
- proportion of patients who are opioid free posttreatment through 72 hours

An approach identical to the primary efficacy analysis will be used for each of the continuous key secondary variables and the same statistics will be presented. For key secondary outcomes of proportions, each proportion, the difference, and 95% confidence intervals (CIs) will be reported; the difference will be tested with the 2-proportion Z test (with Cui-Hung-Wang [CHW] method

Innocoll

Clinical Study Protocol With Amendment 02

Study INN-CB-024

Controlled Study-Postsurgical Analgesia

applied to account for the interim analysis). In the case of low counts (any expected cell count  $\leq 5$ ), a Fisher's Exact test will be used; p-values will be transformed to an equivalent Z for applying the CHW method.

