All continuous secondary efficacy variables will be summarized with appropriate descriptive statistics (sample size, mean, SD, coefficient of variation [CV], median, minimum, maximum, and 25th and 75th percentiles) and analyzed using ANCOVA models with treatment as the main effect and a covariate for BMI.

Summary graphs of efficacy data including TOpA and NPRS scores by treatment group (arithmetic means and standard error [SE]) vs nominal time will be plotted.

All categorical efficacy variables will be summarized with counts and proportions and compared by Cochran-Mantel-Haenszel tests (for ordered variables), Pearson chi-squared, or Fisher's exact tests as needed.

The time to first use of opioid rescue medication, time to discharge from the PACU, and time to no longer using rescue medication during the study will be summarized using Kaplan-Meier methods. Log rank tests will be used to compare treatment groups. The median time to discharge will be estimated together with the associated 95% CI.

Models containing additional blocking factors or covariates may be fit as secondary analyses.

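### Study center is a stratification factor but is missing from the confirmatory SPI model and the opioid-free tests; this may forgo some SPI48 power but does not harm validity

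*Protocol*

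**What the plan says.** Protocol Section 5.10 sets 1:1 allocation and adds: "Patients will be stratified by study center and body mass index (BMI"), with a cut at 30 kg/m². The Synopsis plans up to 8 centers.

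Section 9.5 fixes the SPI24 analysis as an ANCOVA "with treatment as the main effect and a covariate for BMI (continuous"). For SPI48 and SPI72 it states: "An approach identical to the primary efficacy analysis will be used for each of the continuous key secondary variables". For the three opioid-free proportions, "the difference will be tested with the 2-proportion Z test", with Fisher's exact test when expected counts are low. Neither center nor BMI enters those tests. Each test is run separately in the two stages and combined with fixed weights of √0.5.

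Center could enter only through one closing sentence of Section 9.5: "Models containing additional blocking factors or covariates may be fit as secondary analyses".

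On size, Section 9.1 says: "Sample size is estimated at 360 patients, with 180 patients per treatment group". It gives standardized effects of 0.525 for SPI24 and 0.25 for SPI48, and power of at least 66% for SPI48.

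**The concern.** Stratifying by center balances the arms within each center, so differences between centers largely drop out of the treatment contrast. A model without center still counts those differences as residual error. If centers differ in mean SPI, the reported standard error is then larger than the true one: confidence intervals are too wide, p-values too large, and the test rejects less often than its nominal level under the null.

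The place where this could matter is SPI48. It is the first key secondary in the fixed sequence of Section 9.8, so a miss there stops all later testing, and it is planned at only 66% power. The protocol carries one stratification factor into the SPI model and not the other, and gives no reason. Optional secondary models cannot change a confirmatory p-value.

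**Working it through.** **Inputs from the protocol.** n = 360, 180 per group (Section 9.1); d = 0.25 for SPI48 and 0.525 for SPI24 (Section 9.1); level 0.05 (Section 9.8, sidedness not stated); two stages of about 180 patients with weights √0.5 (Sections 9.5 and 9.9).

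**Assumption.** Let r be the share of total SPI variance that lies between centers. The protocol gives no value, so a range from 0 to 0.20 is shown.

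**Step 1: the plan's own figure.** The noncentrality for SPI48 is 0.25 × √360 / 2 = 2.372. Power at two-sided 0.05 is Φ(2.372 − 1.96) = 66.0%, which matches the stated 66%. One-sided 0.05 would give 76.6%, so two-sided is used below.

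**Step 2: effect of leaving center out.** With arms balanced within center, the model without center uses SE = √(2/180) in SD units, while the true SE is √((1 − r) × 2/180). Therefore:

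- SE overstatement: 1/√(1 − r)
- true two-sided level without center: 2 × [1 − Φ(1.96/√(1 − r))]
- power without center: Φ((2.372 − 1.96)/√(1 − r))
- power with center: Φ(2.372/√(1 − r) − 1.96)

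| r | SE ratio | True level without center | SPI48 power without center | SPI48 power with center |
|---|---|---|---|---|
| 0 | 1.000 | 0.050 | 66.0% | 66.0% |
| 0.02 | 1.010 | 0.048 | 66.1% | 66.9% |
| 0.05 | 1.026 | 0.044 | 66.4% | 68.2% |
| 0.10 | 1.054 | 0.039 | 66.8% | 70.5% |
| 0.15 | 1.085 | 0.034 | 67.2% | 73.0% |
| 0.20 | 1.118 | 0.028 | 67.7% | 75.5% |

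For SPI24 (d = 0.525), power is 99.9% or higher in every row, with or without center.

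**Step 3: the gain in patients.** Find the sample size at which the test without center reaches the power of the test with center. This needs a noncentrality of 2.372 + 1.96 × (1 − √(1 − r)). The ratio of sample sizes is the square of that value over 2.372.

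- r = 0.05: (2.421/2.372)² = 1.042, about 4%
- r = 0.10: (2.472/2.372)² = 1.087, about 9%
- r = 0.15: (2.525/2.372)² = 1.133, about 13%

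**Step 4: check by simulation.** The setting was 8 centers, permuted blocks of 4 (assumed) within center by BMI group, two stages of 180 combined with weights √0.5, and 3,000 runs per setting. Power for d = 0.25 without and with center was:

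- r = 0: 0.647 and 0.642
- r = 0.05: 0.656 and 0.672
- r = 0.10: 0.669 and 0.701
- r = 0.20: 0.688 and 0.754

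One-sided type I error without center ran from 0.023 at r = 0 to 0.011 at r = 0.20. The pattern agrees with the formulas. The small deficit for the center model at r = 0 is within simulation error.

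No calculation was made for the opioid-free proportions, because the protocol gives no expected rates.

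**The case against.** The strongest reply is that nothing here breaks the analysis. Under stratified allocation the test without center holds its level, and Section 9 lets the SAP add detail. The protocol also standardizes anesthesia (Section 5.1.1), implant placement (Section 5.1.2) and rescue (Section 5.4), all in US centers, so center differences may be small. All of this stands, except that the SAP argument is only partial: Section 9.5 does not leave the model open, and it classes blocking factors as optional secondary work.

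A reader might infer more than the documents support:

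- **That type I error is inflated.** The direction is the opposite; the true level is at or below nominal.
- **That the primary endpoint is endangered.** At the planned SPI24 effect the difference is negligible. It would matter only if the effect were much smaller than assumed.
- **That SPI48 falls short of its stated power.** It does not: power without center is at or above 66% for every r. What is forgone is an improvement.
- **That the gain is worth 5%, 11% or 18% more patients.** That is 1/(1 − r), the ratio of variances. It ignores that stratified allocation already lowers the true variance of the contrast in the test without center. Step 3 gives about 4%, 9% and 13%.
- **That the omission will cause needless sample-size increases.** Section 9.9 does not name the model behind the interim Z. At the planned SPI24 effect the expected interim Z is 0.525 × √180 / 2 = 3.52, and conditional power by the protocol's formula is Φ(2 × 3.52 − 1.96 × √2), above 99.9%. A larger increase driven by SPI48 is possible, but its probability has not been established.

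It is also fair to say that a fully stratified test of proportions has its own cost. Up to 8 centers by 2 BMI groups is 16 strata, about 11 patients per stratum in a stage of 180, or 5 to 6 per arm.

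**Conclusion.** The point holds as a matter of efficiency, not validity. Center is used in the randomization and left out of every confirmatory test; BMI is carried into the SPI models but not into the opioid-free tests. If center is prognostic, the tests are conservative.

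The cost is negligible for SPI24 at the planned effect. For SPI48 it is about 2, 4 or 6 percentage points of power forgone if center explains 5%, 10% or 15% of the variance, and nothing if center explains none. These sizes rest on an assumed variance share, arms balanced within center, a two-sided 0.05 level and the protocol's d = 0.25. The omission itself is certain; its size is not. The loss for the opioid-free proportions is unquantified. The change is still worth making, because SPI48 gates the later tests, has modest planned power, and the remedy is nearly free.

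**What to change.** Before any unblinded interim data exist, amend Section 9.5 and carry the change into the SAP:

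1. Fit SPI24, SPI48 and SPI72 in each stage by ANCOVA with treatment, study center and continuous BMI. Pool small centers by a prespecified rule applied blind to treatment.
2. State in Section 9.9 that the interim Z comes from this same model.
3. Test the opioid-free proportions in each stage with a Cochran-Mantel-Haenszel test stratified by pooled center and BMI group, with a prespecified rule for sparse strata, and then convert to Z for the CHW combination.
4. Stratifying the log-rank tests is optional, since those variables lie outside the tested sequence.

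The stage weights and the testing order stay as they are. The cost is protocol and SAP wording, at most 7 degrees of freedom per stage of about 180 patients in the ANCOVA, and the need to write the pooling and sparse-strata rules in advance. If the SAP already includes center in the confirmatory models, only the protocol text needs to be aligned.

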## **9.6 Safety and Tolerability Analysis and Planned Method of Analysis**

### **9.6.1 Safety and Tolerability Analysis**

Safety variables include assessment of adverse events, clinical laboratory test results, vital signs measurements (including body temperature, pulse, systolic and diastolic blood pressure, respiration rate, and oxygen saturation measured by pulse oximetry), ECG findings, surgical wound grading, and concomitant medications. These analyses will be conducted for the safety population. No formal statistical tests will be performed on safety evaluations.

Adverse events will be coded using Medical Dictionary for Regulatory Activities (MedDRA), version 18 or later. The number and percentage of patients with adverse events will be displayed for each treatment group by system organ class (SOC) and preferred term. Summaries in terms of severity and relationship to study treatment will also be provided. Serious adverse events will be summarized separately in a similar fashion. In the case of multiple occurrences of the same adverse event for the same patient, the patient will be counted only once for each SOC and preferred term. All adverse events and serious adverse events will be listed by patient.

Adverse events collected from the assessments for systemic bupivacaine toxicity and wound healing will each be presented both as part of the adverse events overall and summarized separately. Additionally, the counts and percentages of patients in category of the Southampton Wound Grading Scale will be reported at each time point where it is collected.

Clinical laboratory test results, vital signs measurements, and any other appropriate quantitative safety data will be presented descriptively by treatment group at each time point for the baseline (screening) and postbaseline evaluations, as well as change from baseline, using descriptive statistics (number, mean, SD, median, minimum, and maximum).

ECG data including RR, PR, QRS, and QTc intervals will be summarized descriptively.

Innocoll

Clinical Study Protocol With Amendment 02

Study INN-CB-024

Controlled Study-Postsurgical Analgesia

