- Adverse events occurring at an incidence of 2% or more patients following administration of INL-001 at 300 mg and at a higher incidence than placebo implants, respectively, were somnolence (19.2% vs 13.9%), dizziness (16.4% vs 13.9%), incision site swelling (13% vs 10.7%), incision site pain (11.7% vs 11.4%), restlessness (7.7% vs 6.8%), dysgeusia (7.5% vs 4.6%), vision blurred (4.9% vs 2.1%), headache (4.7% vs 2.1%), tremor (4.5% vs 2.1%), postprocedural discharge (4.3% vs 3.6%), scrotal swelling (2.8% vs 1.8%), seroma (2.6% vs 1.8%), oral hypoesthesia (2.6% vs 1.4%), pyrexia (2.3% vs 1.8%), and wound dehiscence (2.1% vs 1.8%).
- In these studies, adverse events considered by the investigator to be treatment related following INL-001 placement in the surgical site occurred at a rate of 1.5% or less. The only treatment-related adverse event that occurred in 1% or more of all patients who received INL-001 at 300 mg was dysgeusia (1.3%), which also occurred in 0.7% of patients in the placebo group.
- Across the INL-001 clinical development program, 16 patients experienced 1 or more serious adverse events: 11 patients in the INL-001 (including earlier formulation) treatment group and 5 patients in the placebo implant or other comparator group. Serious adverse events reported in the INL-001 treatment group included wound infection and seroma. One patient had the INL-001 implant removed after placement of an earlier formulation of bupivacaine collagen matrix implant during bladder sling surgery (see event described below).
- There were no verbatim reports of systemic bupivacaine toxicity or LAST during any inguinal hernia repair study done as part of the development program for INL-001. The safety assessments conducted during the development program included monitoring adverse events, measurement of vital signs, and assessments with multiday cardiac Holter monitors. These assessments revealed no constellation of neurologic or cardiovascular (CV) signs or symptoms to suggest systemic bupivacaine toxicity in patients undergoing open inguinal hernia repair receiving INL-001.

One patient experienced signs and symptoms thought to be consistent with LAST approximately 4 hours after administration of an earlier formulation of the INL-001 (at 150 mg) following bladder sling surgery. Treatment included administration of lipid emulsion and surgical removal of the INL-001 implants.

Innocoll

Clinical Study Protocol With Amendment 02  
Study INN-CB-024

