### 1.5 Known and Potential Benefits and Risks to Patients

Complete information may be found in the IB provided to each investigator. Each investigator must become familiar with all information in the IB before commencing this study.

The potential benefits to participating patients with acute postsurgical pain following abdominoplasty are (1) that they may experience a reduction in acute postoperative pain as a result of treatment with INL-001, (2) that they will understand they are contributing to the scientific knowledge that may lead to expansion of the treatment options for patients' acute postsurgical pain, and (3) because INL-001 is implanted (not injected) into the surgical site, accidental intravascular injection/surgical site infiltration that often leads to bupivacaine's most serious potential central nervous system (CNS) and CV systemic toxicities may be prevented.

The potential risks of study participation include those associated with exposure to INL-001 per the FDA-approved labeling and the risks of medical evaluation, including venipuncture and other risks associated with the required medical procedures.

Because individual patient factors may impact the safety of an amide local anesthetic such as bupivacaine, there is a potential risk for severe life-threatening adverse effects associated with the local administration of bupivacaine. Therefore, INL-001 should be administered in a setting where trained personnel and equipment are available to promptly treat patients who show evidence of CNS or CV toxicity. Monitoring cardiovascular and neurologic status, as well as vital signs, should be performed during and after placement of INL-001.

Allergic-type reactions are rare and may occur as a result of sensitivity to bupivacaine or to other formulation ingredients. These reactions are characterized by signs of urticaria, pruritus, erythema, angioedema (including laryngeal edema), tachycardia, sneezing, nausea, vomiting, dizziness, syncope, excessive sweating, elevated temperature, and possibly anaphylactoid-like symptoms (including severe hypotension). Cross-sensitivity among members of the amide-type local anesthetic group has been reported.

Innocoll

Clinical Study Protocol With Amendment 02

Study INN-CB-024

Controlled Study-Postsurgical Analgesia

---

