#### **4.3.2 Assessment of Bupivacaine Toxicity and Removal of Implants Due to Bupivacaine Systemic Toxicity**

Patients in this study will be domiciled in a monitored setting at least through 72 hours posttreatment. In addition to the general adverse event monitoring in this setting, patients will be specifically queried and assessed for signs and symptoms potentially indicative of systemic bupivacaine toxicity at multiple time points during the study using the following list of signs and symptoms:

- respiratory difficulty
- change in level of consciousness
- restlessness
- anxiety
- difficulty speaking or being understood
- lightheadedness
- numbness and tingling of the mouth and lips
- metallic taste
- tinnitus (ringing in ears)
- dizziness
- changes in vision
- tremors
- depression
- drowsiness

Assessment of patients for signs and symptoms potentially indicative of systemic bupivacaine toxicity will be made after Time 0/implantation at the following time points: 0.5, 1, 2, 3, and 4 hours (each  $\pm 15$  minutes); 5, 7, 9, 12, 15, 18, 24, 48, and 72 hours (each  $\pm 1$  hour); and on days 7 and 15.

Innocoll

Clinical Study Protocol With Amendment 02

Study INN-CB-024

Controlled Study-Postsurgical Analgesia

If any of these signs or symptoms are assessed (and recorded) as an adverse event(s), the severity of the adverse event(s) will be scored based on the adverse event grading scale of the Common Terminology Criteria for Adverse Events (CTCAE) version 5.0 as follows:

Grade	Description
1	Mild ; asymptomatic or mild symptoms; clinical or diagnostic observations only; intervention not indicated
2	Moderate ; minimal, local, or noninvasive intervention indicated; limiting age-appropriate instrumental activities of daily living
3	Severe or medically significant but not immediately life-threatening; hospitalization or prolongation of hospitalization indicated; disabling; limiting self care activities of daily living
4	Life-threatening consequences ; urgent intervention indicated
5	Death related to adverse event

If a patient experiences a grade 4 adverse event of any of the following:

- respiratory difficulty
- change in level of consciousness
- cardiovascular event
- 3 or more of the other signs and symptoms on the list concurrently

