##### 7.1.6.1 Assessment of Signs and Symptoms Potentially Indicative of Systemic Bupivacaine Toxicity

Patients will be specifically queried and assessed by the investigator/subinvestigator (physician) for these signs and symptoms potentially indicative of bupivacaine toxicity at specified time points after implantation of study drug using the following list of signs and symptoms (see [Table 1](#)).

Have you had any of the following since we last spoke?

- respiratory difficulty
- change in level of consciousness
- restlessness
- anxiety
- difficulty speaking or being understood
- lightheadedness
- numbness and tingling of the mouth and lips
- metallic taste
- tinnitus (ringing in ears)
- dizziness
- changes in your vision
- tremors
- depression
- drowsiness

If a patient reports any of the above signs and symptoms, they will be assessed as to whether they qualify as adverse events and, if so, recorded as noted previously regarding adverse events. If the investigator determines that the patient experienced systemic bupivacaine toxicity, this will be recorded as an adverse event.

If any of these signs or symptoms are assessed (and recorded) as an adverse event(s), the severity of each adverse event must be recorded according to CTCAE (see [Section 4.3.2](#)).

Innocoll

Clinical Study Protocol With Amendment 02

Study INN-CB-024

Controlled Study-Postsurgical Analgesia

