### 7.1.6.3 Wound Grading

At 72 hours posttreatment, day 15, and day 30 the investigator/subinvestigator (physician) will complete the Southampton Wound Grading System. Investigator judgment will be used to determine if a finding is an adverse event. If an adverse event is identified during completion of this assessment that was not previously identified through the wound healing assessment, it will be assessed and recorded according to the adverse event criteria defined above.

Innocoll

Clinical Study Protocol With Amendment 02

Study INN-CB-024

Controlled Study-Postsurgical Analgesia

Wound healing grade and appearance will be assessed as follows:

Grade	Appearance
0	Normal healing
I Normal healing with mild bruising or erythema:	
a	Some bruising
b	Considerable bruising
c	Mild erythema
II Erythema plus other signs of inflammation:	
a	At one point
b	Around sutures
c	Along wound
d	Around wound
III Clear or haemoserous discharge:	
a	At one point only ( $\leq 2$ cm)
b	Along wound ( $> 2$ cm)
c	Large volume
d	Prolonged ( $> 3$ days)
	Major complications
IV Pus:	
a	At one point only ( $\leq 2$ cm)
b	Along wound ( $> 2$ cm)
V Deep or severe wound infection with or without tissue breakdown; haematoma requiring aspiration	

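### Section 9.6.1 picks events for the toxicity and wound summaries by the assessment that collected them, so relevant events found another way can be left out

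*Protocol*

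**What the plan says.** Protocol section 7.1.6 names two safety areas of interest, systemic bupivacaine toxicity and wound healing, and gives a list of signs and symptoms for each. Section 9.6.1 sets the tabulation rule: "Adverse events collected from the assessments for systemic bupivacaine toxicity and wound healing will each be presented both as part". The rest of that sentence puts these events in the full adverse event display and also in tables of their own.

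- **Toxicity.** Under section 7.1.6.1 patients are queried "at specified time points after implantation of study drug using the following list of signs and symptoms". The list, repeated in section 4.3.2, has 14 items. Section 1.5 asks for a setting equipped to "promptly treat patients who show evidence of CNS or CV toxicity", and section 4.3.2 includes a "cardiovascular event" among its grade 4 criteria.
- **Wound.** Section 7.1.6.2 has nine items, five of which are always recorded as adverse events. Section 7.1.6.3 adds Southampton grading and provides for an adverse event found there "that was not previously identified through the wound healing assessment, it will be assessed and recorded according to the adverse event criteria". On earlier experience, section 1.4.2 states: "Serious adverse events reported in the INL-001 treatment group included wound infection and seroma".
- **Overall display.** Section 9.6.1 also says: "The number and percentage of patients with adverse events will be displayed for each treatment group by system organ class (SOC) and preferred term".

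**The concern.** A special-interest table is where a reader looks first for a specific harm. If entry depends on how an event came to light, two identical events can be treated differently: one elicited by the checklist is counted, and one reported spontaneously or found on examination is not.

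This matters most for toxicity. Section 1.1 gives safety in relation to systemic absorption, in a more vascular operation, as one reason for choosing abdominoplasty. The protocol regards cardiovascular effects as part of bupivacaine toxicity, but the checklist that feeds the toxicity table does not ask about them. For the wound, the protocol itself foresees adverse events that the wound healing assessment misses, and section 9.6.1 does not place them in the wound summary.

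The rule is also hard to apply. Section 7.1.2.4 lets adverse events arrive by open-ended question or telephone call, and has a diagnosis recorded in place of its symptoms. Its list of recorded adverse event details contains no field for the assessment that found the event (the CRF is not shown). Two programmers could reasonably build different tables.

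**Working it through.** The protocol states no figure on this point, so the check is mainly a comparison of sections.

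**Step 1. Toxicity list against recognised toxicity.**

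| Source | Cardiovascular content |
|---|---|
| Checklist, sections 4.3.2 and 7.1.6.1 (14 items) | 0 items |
| Benefit-risk, section 1.5 | cardiovascular toxicity named with CNS toxicity |
| Earlier hernia studies, section 1.4.2 | neurologic and cardiovascular signs both considered |
| Grade 4 criteria, section 4.3.2 | a cardiovascular event is one criterion |

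In section 4.3.2 the cardiovascular criterion is followed by a bullet about the remaining signs on the list, although the list has no cardiovascular entry. The section does not agree with itself on what the list covers.

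**Step 2. Routes for a cardiovascular event into the toxicity summary.**

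- Diagnosed by the investigator as systemic toxicity: recorded as an adverse event under section 7.1.6.1, so it enters.
- Traced from a checklist symptom such as dizziness: may enter under its diagnosis (section 7.1.2.4).
- Isolated, found from vital signs, ECG or spontaneous report, and not diagnosed as toxicity: no route on the wording of section 9.6.1. The only scheduled post-treatment ECG is on day 30 (Table 1), so within the first 72 hours vital signs and spontaneous report are the likelier sources.

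**Step 3. Routes for a wound event into the wound summary.**

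- Fluid leakage, wound-edge separation, a provider visit about the wound, antibiotics for wound infection, or admission for wound infection: always an adverse event, so it enters.
- Pain, redness, warmth or swelling: enters if judged an adverse event.
- Seroma: not named, but at least three items (leakage, swelling, provider visit) can capture it.
- Found only at Southampton grading: not collected from the wound healing assessment, so no route on the wording.

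**Step 4. Scale, using seroma as illustration.** Inputs: 2.6% on INL-001 300 mg and 1.8% on placebo (section 1.4.2); 180 patients per group (section 3.2). Assumption: earlier rates carry over to abdominoplasty, for which the protocol gives no rate.

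Total expected = n × rate: 180 × 0.026 = 4.7 on INL-001 and 180 × 0.018 = 3.2 on placebo.

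Let s be the share recorded outside the wound checklist, which the documents do not give. The wound summary would then show n × rate × (1 − s):

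| s | INL-001 | Placebo |
|---|---|---|
| 0% | 4.7 | 3.2 |
| 25% | 3.5 | 2.4 |
| 50% | 2.3 | 1.6 |
| 75% | 1.2 | 0.8 |
| 100% | 0 | 0 |

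The range runs from all captured to none captured. The figures 4.7 and 3.2 are total expected seromas, not missed ones.

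**The case against.** The strongest reply is that this is detail for the SAP. Section 9 leaves further analysis detail to that document, preferred-term groupings are ordinary SAP content, and section 9.6.1 does not expressly exclude events found elsewhere. This stands in part: the SAP may already resolve the matter. But the protocol is not silent. It states a selection rule, and an SAP that follows it inherits the gap.

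A reader might infer that the toxicity summary could never show cardiovascular toxicity. The documents do not support that, because investigator-diagnosed toxicity is recorded under section 7.1.6.1 and a checklist symptom can be entered under a cardiovascular diagnosis. Nor do they support calling cardiovascular toxicity an observed harm of the implant: section 1.4.2 reports no neurologic or cardiovascular pattern suggesting toxicity in the hernia studies. It is a recognised risk.

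A reader might also infer that seroma drops out of the wound summary. It does not have to, as step 3 shows.

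The room for grading-only wound events is limited. A physician does the wound healing assessment at the same 72-hour, day 15 and day 30 visits as the grading. Section 9.6.1 also tabulates the Southampton categories, which include discharge, pus, deep infection and haematoma requiring aspiration. That table reports grades, however, and does not bring the adverse events into the wound summary.

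Finally, nothing disappears from the report. All adverse events remain in the tables by system organ class and preferred term and in the listings, and vital signs and ECG data are summarised by group. The seroma rates come from a programme in which 816 of 892 patients (91%) had hernia repair. All of this stands, and it limits the size of the point.

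**Conclusion.** The point holds in a limited form. As worded, section 9.6.1 selects the two special-interest summaries by source, so they can undercount. The clearer gap is an isolated cardiovascular adverse event not diagnosed as systemic toxicity; the second is a wound adverse event found only at Southampton grading. The conclusion rests on reading the rule as written, without sight of the SAP or the CRF.

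The number of events affected cannot be derived from the documents. The effect is on the completeness and reproducibility of two descriptive tables. No data are lost, and no formal test is involved, since none is planned for safety. It is a cheap improvement worth making, not a threat to the trial's conclusions.

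**What to change.** In section 9.6.1, define both summaries by prespecified MedDRA terms, regardless of how the event was found (checklist, Southampton grading, vital signs, ECG, physical examination or spontaneous report).

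- **Toxicity summary:** terms for the 14 checklist items, cardiovascular terms, and investigator-diagnosed systemic toxicity.
- **Wound summary:** terms for the nine checklist items, wound events detected at Southampton grading, seroma and haematoma.
- **Checklist-sourced tables:** keep them as a labelled subset, with a stated rule for deciding that an event came from a checklist.

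Separately, the cardiovascular criterion in section 4.3.2 and the 14-item list, which does not contain it, must be reconciled. Which of the two should change is for the sponsor to decide.

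The cost is a wording change and two term lists, fixed before unblinding. The events are already recorded as adverse events, so the tabulation change needs no new assessment. The downside is that special-interest incidence may be somewhat higher and less specific, because some cardiovascular or wound terms will have causes other than the implant. The subset table lets a reader see how much of any increase comes from the wider definition.
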